4.7 Recruitment and identification of potential participants

Prior to starting the study a comprehensive recruitment plan will be developed. The study will be advertised across the Melbourne Children's Campus (MCRI, Royal Children's Hospital, University of Melbourne), Royal Melbourne Hospital, the Doherty Research Institute, the Parkville precinct and, the broader Melbourne community. We will initially target people working in the medical, science, and healthcare fields and expand recruitment to the general public as needed. We will target specific study or age groups as needed as the study proceeds. Study information (via email, healthcare facilities notice board and/or website/social media, patient/participant registries and recruitment services etc.) will include an information sheet about the study and a link to the study website where they can evaluate their eligibility and obtain additional study details, such as the participant information sheet and consent form (PICF). The potential participant can register their interest and will be given the opportunity to talk with a research team member by phone or zoom if they have any further questions.

All potential participants will be recorded on a recruitment/enrolment log. No identifying information will be retained if the potential participant decides not to participate.

In addition, participants will also be recruited directly from interested general practices. Potentially eligible participants will be sent an email or SMS with the study details from their GP practice and be given the option to contact the COVID-19 booster study team if they want more information or wish to join the study. The COVID-19 booster study team will not have access to GP patient records. In select cases satellite clinics may be conducted at GP clinics with facilities to conduct vaccinations. Similarly at community clinics with access to medical facilities.

Participants from other relevant MCRI studies (for example the BRACE trial), who consented to be contacted for future research, will be contacted by the original study teams. The original study team will send the participants an email with the study details and give them the option to contact the COVID-19 booster study team if they want more information or wish to join the study. The COVID-19 booster study team will not have access to the participant details.

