6 RANDOMISATION AND BLINDING

The two vaccine groups will be randomised 1:1 to one of two interventions (bivalent Omicron-specific Moderna and Novavax) stratified by age (<50 and \geq 50 years). An independent statistician from the Melbourne Children's Trial Centre at the Murdoch Children's Research Institute will provide a secure, password-protected web-based randomisation schedule. Blocked randomisation will be used with random blocks of permuted length.

50% of participants from each vaccine group will be included in the cell-mediated immunity (CMI) subgroup analysis. We will ensure that the age strata (<50 and \geq 50 years) are equally represented in the CMI vaccine groups. As only 10-20 CMI samples can be processed per day, we will recruit the first 10-20 participants per day to participate in this substudy.

The control group will not be randomised and will be recruited from participants <60 years of age who indicate that they are not planning to receive a fourth vaccine dose at the time of recruitment. Controls will be recruited into proportional predefined age bands (18-29 years, 30-49 years, 50-59 years).

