11.3.2. Secondary outcomes

Binding antibodies - changes from baseline will be expressed as geometric mean fold ratios (GMFR), calculated as the ratio of the post-booster GMC to the baseline GMC. GMCs will be compared between the two vaccine groups and between the vaccine and control groups at 6, 12, 18, 24 and 30 months. We will account for age in the analysis.

Functional antibodies seven time points for vaccine groups [baseline, 1, 6, 12, 18, 24 and 30 months] and six time points for controls [baseline, 6, 12, 18, 24 and 30 months] – for the C-PASS assay (sVNT), data are reported as percentage (%) inhibition by neutralising antibodies using the manufacturer’s instructions. A <30% inhibition is considered negative, while ≥30% inhibition is considered positive. Data will be presented as mean and standard deviation.

Neutralizing assay (20% subset of samples at all time points) up to 12 months – Data will be reported as endpoint titre calculated using the Reed/Muench method (23). A titre of 10 reflects undetectable neutralizing activity.

Cellular immunity: (on a 50% subset at seven time points for vaccine groups and six time points for controls)

Quantiferon COVID IFNy release assay up to 12 months – Levels of IFNy will be reported in IU/ml according to the manufacturer’s instructions. Data will be reported as GMT and 95% confidence intervals.

IFNy Elispot – The number of IFNy-producing cells/million PBMCs will be reported using means and 95% confidence intervals.

Intracellular cytokine staining – The data will be reported as the frequency (%) of cytokine-expressing T cells (e.g., total T cells, CD4 T cells, CD8 T cells). Cytokines such as IFNy (Th1) and IL-5 (Th2) will be measured as a minimum. This will be presented as means and 95% confidence intervals.

Multiplex cytokine assays – A 10-plex panel of cytokines will be measured in supernatants from the Elispot studies. Cytokine concentrations will be reported in pg/ml, and data will be presented as GMT and 95% confidence intervals.

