4.9 LIST OF NECESSARY VARIABLES

Below is a list of necessary variables that need to be cleaned and locked for the analysis of each immunological endpoint to be triggered, in addition to the immunological parameter itself:

- Trial arm
- Primary series vaccine
- First booster vaccine
- Age group strata
- Dates of first, second and third doses
- Date of trial vaccine for vaccine groups (Day 0)
- Date of blood-draw/study visit
- Reactogenicity for all solicited reactions on 7 days, including grading (Day-28 timepoint only)
- SARS-CoV-2 infection, including clinical spectrum and date of positive test (to relevant timepoint)
- Receipt of additional COVID-19 vaccine doses (yes/no, and date) (to relevant timepoint)
- Adverse events (severity, causality, SOC, seriousness, expectedness, and outcome) (to relevant timepoint)
- Baseline value of the immunological parameter to be analysed

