8 ANALYSIS OF THE SECONDARY OUTCOMES

8.1 ANALYSIS OF SECONDARY IMMUNOLOGICAL ENDPOINTS

Table 8 lists the secondary immunological endpoints, including the timepoint measured, population measure, groups being compared and the measure of association between groups. Note there may be additional secondary immunological outcome variables (e.g. relating to new variants of concern) that become available after this SAP is written. These additional variables will be analysed in the same way as other secondary immunological variables listed in Table 8, with analysis dependent on the distribution (e.g. whether symmetrical).

Table 8. Secondary immunological endpoints

Outcome	Population measure	Measure of association	Timepoint	Comparisons
Binding antibody				
Binding antibody (IgG) (Wuhan) BAU/ml	GM (95% CI)	GMR (95% CI)	Month-6	Group A vs B, Group A vs control, Group B vs control
			Month-12	Group A vs B, Group A vs control, Group B vs control
			Month-18	Group A vs B, Group A vs control, Group B vs control
			Month-24	Group A vs B, Group A vs control, Group B vs control
			Month-30	Group A vs B, Group A vs control, Group B vs control
Binding antibody (IgG) (Omicron BA.1), RU/ml	GM (95% CI)	GMR (95% CI)	Day-28	Group A vs B
			Month-6	Group A vs B, Group A vs control, Group B vs control
			Month-12	Group A vs B, Group A vs control, Group B vs control
			Month-18	Group A vs B, Group A vs control, Group B vs control
			Month-24	Group A vs B, Group A vs control, Group B vs control
			Month-30	Group A vs B, Group A vs control, Group B vs control
Binding antibody (IgG) (Omicron BA.4/5), EU/ml	GM (95% CI)	GMR (95% CI)	Day-28	Group A vs B
			Month-6	Group A vs B, Group A vs control, Group B vs control
			Month-12	Group A vs B, Group A vs control, Group B vs control
			Month-18	Group A vs B, Group A vs control, Group B vs control
			Month-24	Group A vs B, Group A vs control, Group B vs control
			Month-30	Group A vs B, Group A vs control, Group B vs control
Binding antibody (IgG) (Omicron JN.1), EU/ml	GM (95% CI)	GMR (95% CI)	Day-28	Group A vs B
			Month-6	Group A vs B, Group A vs control, Group B vs control
			Month-12	Group A vs B, Group A vs control, Group B vs control
			Month-18	Group A vs B, Group A vs control, Group B vs control
			Month-24	Group A vs B, Group A vs control, Group B vs control
			Month-30	Group A vs B, Group A vs control, Group B vs control
Functional antibody				
Functional antibody sVNT (Wuhan), U/ml	GM (95% CI)	GMR (95% CI)	Day-28	Group A vs B

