Handling of intercurrent events	Handling of missing data The proportion of participants excluded due to missing outcome or covariate data will be described by study group. If >5% of participants are excluded due to missing data, a supplementary analysis will be performed with multiple imputation.
Population-level summary measure Geometric mean ratio (GMR) OR Difference in Means*	Analysis approach Linear regression will be used to estimate the difference in mean [OUTCOME]* between the vaccine arms, adjusted for the stratifying variable (age group), primary series and first booster vaccine, and baseline [OUTCOME]* levels. Where the population-level summary measure is the GMR, the outcome variable (and the baseline value) will be log_e transformed before regression, and the GMR (95% CI) will be calculated as the antilogarithms of the mean difference (β_1) and its 95% CI. When zero and negative values are expected, the population-level summary measure will be the difference in medians. This will be estimated using quantile regression with the same adjustment variables as above. The distribution of the immunological data at each timepoint will be displayed using a scatterplot

	overlaid with median and interquartile range (see Dummy Figure 3)
--	---

*This table is generic for all secondary Month-6 and Month-12 immunological endpoints (see Table 8), which will be analysed in the same way depending on their distributions; the population measure for outcomes with skewed distributions is the geometric mean and the population-level summary measure of association (MoA) is the GMR – baseline and Month-[6/12] values will be log_e transformed before analysis; the population measure for normally distributed outcomes is the mean and the population-level summary measure of association (MoA) is the Difference in Means. For outcomes with skewed distributions and negative values, the population summary measure of association is the difference in medians, which will be estimated using quantile regression.

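### No vaccine-versus-control model is specified for Months 6–30, and the only model offered has no enrolment date, so staggered enrolment of the non-randomised controls would confound those contrasts

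*SAP*

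**What the plan says.** SAP 8.1, Table 8, lists "Group A vs B, Group A vs control, Group B vs control" for binding and functional antibodies at Months 6, 12, 18, 24 and 30, and for neutralising antibody and IFN-γ at Months 6 and 12. Each has an estimate and a 95% CI: a GMR, or for IFN-γ possibly a difference in medians. Protocol 11.3.2 agrees for binding antibody: "GMCs will be compared between the two vaccine groups and between the vaccine and control groups at 6, 12, 18, 24 and 30 months". Its only adjustment there is "We will account for age in the analysis".

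The analysis for these visits is in SAP 8.1.1, Table 10, which is declared generic for the endpoints in Table 8. Its sentence begins "Linear regression will be used to estimate the difference in mean [OUTCOME]* between the vaccine arms" and continues "adjusted for the stratifying variable (age group), primary series and first booster vaccine, and baseline [OUTCOME]* levels". The estimand, study arms and analysis set in that table cover only the randomised Moderna and Novavax participants. No calendar or enrolment date appears.

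On recruitment, Protocol section 6 states: "The control group will not be randomised and will be recruited from participants <60 years of age". Protocol 4.7 adds: "We will target specific study or age groups as needed as the study proceeds". The synopsis gives a recruitment period of about 4–6 months. The cells in Protocol 6.1 and SAP Table 1 put every Group A participant aged 50 or over on the later BA.4-5 product.

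SAP 6.5 says breakthrough infection boosts the immunological markers. Table 10 nevertheless targets the effect irrespective of infection, so post-infection values are kept.

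**The concern.** Visits are timed from each person's Day 0. Two people at the same nominal visit may therefore have lived through different epidemic periods if they enrolled in different months. Blocked, age-stratified randomisation protects A versus B. Nothing equivalent protects A versus C or B versus C.

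Age adjustment does not restore the alignment. Vaccinees aged 50 or over are planned for the later product period: Group A by the cell table, and Group B by implication, since the two arms are randomised together within age strata. No timing is set for controls aged 50–59. Baseline level reflects infection before Day 0, not after it.

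Under treatment policy, infection that differs because of vaccination belongs to the effect. Infection that differs only because of enrolment month does not; it is confounding. It could appear as a fourth-dose effect or hide one, and Dummy Table 1 would not reveal it because it has no enrolment date.

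**Working it through.** **1. The plan's own figure.** Inputs from Protocol 11.1 are CV 1.15, GMR 1.4, 90% power and two-sided 0.05. Log SD = √ln(1 + 1.15²) = 0.918. n = 2 × (1.960 + 1.282)² × 0.918² / (ln 1.4)² = 157 per group, against 160 stated; 160 / 0.8 = 200. The stated figure is reproduced and 0.918 is used below. It concerns A versus B at Day 28; no sample size is stated for the control contrasts.

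**2. Size of a timing effect.** Suppose infection multiplies the titre by F, and timing alone makes the infected share differ by d. The mean log difference is then d × ln F, so the GMR is off by a factor F^d (or its reciprocal if controls meet more infection). The documents give neither F nor d; both are assumed.

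| d | F = 2 | F = 3 | F = 5 |
|---|---|---|---|
| 0.05 | 1.04 | 1.06 | 1.08 |
| 0.10 | 1.07 | 1.12 | 1.17 |
| 0.20 | 1.15 | 1.25 | 1.38 |

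**3. Effect on the interval.** With 225 vaccinees and 150 controls, SE = 0.918 × √(1/225 + 1/150) = 0.097. With no vaccine effect and F = 4, the 95% CI excludes 1 in 11%, 30% and 82% of trials for d = 0.05, 0.10 and 0.20. For masking, take F = 4 and 20 points more infection in controls: a true GMR of 1.4 is expected to appear as 1.4 / 4^0.20 = 1.4 / 1.32 = 1.06, and power falls from over 90% to about 9%.

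**4. Simulation at Month 6, no vaccine effect.** Assumptions: 180 vaccinees and 120 controls (20% loss), one wave centred at calendar month 5 (SD 1 month), 50% attack rate, a 6-month enrolment window, 800 runs per scenario. A 2-month shift means vaccinees enrol in months 0–4 and controls in months 2–6; a 1-month shift means 0–5 and 1–6. The adjusted model adds enrolment-month terms. Results are for F = 2 / 4 / 8.

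| Shift | GMR, no date | CI excludes 1 | GMR, with month | CI excludes 1 | SE without → with month |
|---|---|---|---|---|---|
| 0 | 1.00 / 1.00 / 1.00 | 4–6% | 1.00 / 1.00 / 1.00 | 4–6% | unchanged |
| 1 month | 1.05 / 1.09 / 1.14 | 7–15% | 1.00 throughout | 4–6% | F = 4: 0.124 → 0.138 |
| 2 months | 1.08 / 1.18 / 1.27 | 12–35% | 1.00–1.01 | 5–7% | F = 4: 0.124 → 0.174 |

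The SE rises by about 11–13% with a 1-month shift and about 40% with a 2-month shift. The simulation covers one visit and one wave, and does not let infection before enrolment raise the baseline titre.

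**5. Existing safeguards.** SAP 9.5 plans subgroups by BA.1 versus BA.4/5 period, but does not adjust the pooled contrast. Table 12 reports breakthrough risk for all three groups by visit interval, repeated with spike and N-protein serology, but not by calendar date. Table 14's hypothetical-strategy estimands compare only the two vaccine groups. None aligns the control contrasts in calendar time.

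**The case against.** The strongest reply is that Table 10 was never the control model. Its estimand, arms and analysis set exclude Group C, so faulting it for lacking a date misses its purpose. That is right as to wording, and it is why the point is put as a missing vaccine-versus-control model. The gap remains, because Table 8 promises estimates that no other passage says how to obtain.

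Second, a reader might infer that controls were enrolled at a different time from vaccinees. The documents do not show this. Calling Group C a separate arm does not mean separate timing, and targeting in Protocol 4.7 is conditional. Staggering is permitted, not recorded.

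Third, a reader might infer that these ratios carry the trial's answer on a fourth dose over three. Protocol 3.1.2 assigns that question to cell-mediated immunity and sets out only to describe antibodies against controls. Table 8 lists IFN-γ against control only at Months 6 and 12, possibly as a difference in medians, to which the factors above do not apply.

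Fourth, 1.38 is the corner of an assumed grid and exceeds every simulated value. A shift within a 4–6 month window is also a shrinking part of cumulative exposure by Months 18–30, although a recent wave could still matter. Both points stand. The baseline adjustment, the three-month infection exclusion and the breakthrough tables also give partial protection or visibility, without correcting the estimate.

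**Conclusion.** The point holds as a conditional one. The SAP plans non-randomised contrasts with confidence intervals, gives no model written for them, and the one generic model has no enrolment date. If enrolment was concurrent, the bias from this source is nil. If it was shifted by 1–2 months, the simulated Month-6 antibody GMR is off by a factor of 1.05–1.27 for 2- to 8-fold boosts. The simple formula gives 1.04–1.38 for 5–20 points and 2- to 5-fold boosts. Boosts, attack rate, wave shape and shift are all assumptions; no bias of a given size is shown for the later visits.

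It would be tempting to say the bias reaches the sponsor's clinically important difference. The documents do not support that: 1.4 was set for Day-28 IgG between vaccine arms, not for contrasts with controls. Nor does the point touch A versus B. It merits a change to the SAP because the remedy uses data already collected and removed the simulated bias.

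**What to change.** - Specify a separate model for A versus control and B versus control: the Table 10 covariates plus calendar date of enrolment, as month or a spline. Use quantile regression with the same terms where medians are compared. State the estimand and an analysis set that includes Group C.
- Add a supplementary analysis restricted to months in which both controls and vaccinees were enrolled. If overlap is limited, make this the main basis for interpretation.
- Report enrolment month by group in Dummy Table 1.
- Adjust for enrolment date rather than infection: vaccination can affect infection, so conditioning on it would depart from treatment policy.
- Leave the randomised A versus B model unchanged.

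The cost is SAP wording. The dates are already on the list in SAP 4.9 ("Date of blood-draw/study visit"). Precision loss is small if enrolment was concurrent, but the SE rises by about 11–13% with a 1-month shift and about 40% with a 2-month shift. Without overlap, no model can separate group from date, and the report should say so.

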8.2 ANALYSIS OF SECONDARY SAFETY ENDPOINTS

Table 11 specifies the secondary safety endpoints, including the timepoint measured, population measure, groups being compared and the measure of association between groups (where relevant).

Table 11. Safety endpoints

Safety Endpoint	Outcome	Timepoint	Population measure	Comparison	Measure of association
i.	Any [#] AE to Day 28 (inclusive)*	28 days post-booster	Frequency [N (%)]	Group A vs Group B	Descriptive only
ii.	Any [#] AE to Day 28 (inclusive)* [^] by severity	28 days post-booster	Frequency [N (%)]	Group A vs Group B	Descriptive only
iii.	Any [#] AE to Day 28 (inclusive)* [^] by causality assessment	28 days post-booster	Frequency [N (%)]	Group A vs Group B	Descriptive only
iv.	Any AE to Day 28 (inclusive)* by SOC and severity [^]	28 days post-booster	Frequency [N (%)]	Group A vs Group B	Descriptive only
v.	Duration [#] of AE to Day 28 (inclusive)* by SOC [^]	28 days post-booster	Median days {25 th – 75 th percentile}, min - max	Group A vs Group B	Descriptive only
vi.	Day of AE onset (days post-booster) to Day 28 (inclusive)* by SOC [^]	28 days post-booster	N by Day	Group A vs Group B	Descriptive only
vii.	AE to Day 28 (inclusive)* by Outcome ^{**^}	28 days post-booster	Frequency [N (%)]	Group A vs Group B	Descriptive only
viii.	Medically attended unsolicited AE to Month-3 visit (inclusive)	90 days post-booster	Frequency [N (%)]	Group A vs Group B	Descriptive only
ix.	SAE to study-end by SOC and expectedness [^]	Month-12 visit	Frequency [N (%)]	Group A vs Group B	Descriptive only
x.	SAE to study-end by Outcome ^{**^}	Month-12 visit	Frequency [N (%)]	Group A vs Group B	Descriptive only

[#]The Safety analysis will only include unsolicited adverse events; solicited adverse events are considered in the Reactogenicity analysis. *Adverse events within 28 days inclusive will be considered, rather than all adverse events before the Day-28 visit, which can occur between 28- and 35-days post-booster. **Outcome categories are Resolved, Resolved with sequelae, Ongoing, Fatal and Unknown; denominator is the total number of SAEs rather than the number of participants. [^]Recurrent events in the same individual will be counted as a single event (using information from the most severe occurrence); all recurrences will be included in the line list of all adverse events. [#] The duration of 'Ongoing' adverse events will be the number of days between the onset and the last visit.

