8.3 Documentation of AEs

The AE will be described in the source documents (e.g., electronic or paper diary card) and captured on the eCRF and will include:

- A description of the AE
- The onset date, duration, date of resolution
- Severity (mild, moderate, or severe – how does the event impact the participant's daily life?)
- Seriousness (i.e., is it an SAE?)

- Any action taken (e.g., treatment, follow-up tests)
- The outcome (recovery, death, continuing, worsening)
- The likelihood of the relationship of the AE to the trial treatment (Unrelated, Possible, Probable, Definite)

Changes in the severity of an AE will be reported. AEs characterised as intermittent will be documented for each episode. All AEs will be followed to adequate resolution, where possible.

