6.3 REACTOGENICITY AND SAFETY OUTCOMES

Table 4 summarises the reactogenicity and safety outcomes and relevant parameters. Further details on all collected parameters are stored in RedCAP Codebooks, as detailed in the Data Management Plan. Definitions of the terms adverse event, adverse reaction, and serious adverse event are given in the Protocol and are aligned with definitions used in trials involving investigational medicinal products.

Table 4. Reactogenicity and safety outcomes

Outcome	Parameter	Categories	Timepoints
Reactogenicity (local)	Pain		

Reactogenicity (general/systemic)	Tenderness	Grade 0, 1, 2, 3, or 4*	Day 1, 2, 3, 4, 5, 6, & 7
	Redness		
	Swelling		
	Hardness		
	Axillary lymphadenopathy		
	Warmth	Binary (presence/absence)	
	Itch		
	Fever		
Adverse Events to 28 Days	Nausea	Grade 0, 1, 2, 3, or 4*	Adverse Events to 28 Days: Day-0, -1, -7, and -28 visits, and Month-3 visit (for new information, e.g., resolution)
	Vomiting		
	Diarrhoea		
	Headache		
	Fatigue/Malaise		
	Myalgia		
	Arthralgia		
	Experienced an adverse event	Binary (yes/no)	
Adverse Reaction to 28 Days ^δ	System Organ Class [^]	As per MedDRA	Serious Adverse Events to 12 months: Unscheduled (participants instructed to contact study staff)
	Severity	Severity Grade 1 (mild), 2 (moderate), 3 (severe), 4 (life-threatening), 5 (fatal) [#]	
	Outcome	1-Resolved 2-Resolved with sequelae 3-Ongoing 4-Fatal 5-Unknown	
	Serious	Binary (yes/no)	
	Onset (days from trial vaccination)	Continuous	
	Event duration (days)	Continuous	
	Relatedness	1-Unrelated 2-Possible 3-Probable 4-Definite	

*5-point severity scale: 0-None; 1-Mild; 2-Moderate; 3-Severe; 4-Life-threatening. Refer to Protocol for more detailed definitions [#]Grade 3-4 events may be SAEs; all Grade 5 events are automatically considered SAEs. [^]Will require derivation from 'event_term' and 'saefin' fields by study team. ^δAn adverse reaction is an adverse event with causality assessment of either Possible, Probable, or Definite.

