10.1.2 Dummy Tables and Figures - Supplement

Dummy Table S 1. Numbers of participants who received an additional COVID-19 vaccine dose by study group and study period

	Moderna (N = n)	Novavax (N = n)	Control (N = n)	Total (N = n)
Received additional dose (Total)	N (%)	N (%)	N (%)	N (%)
Before Month-6 visit	N (%)	N (%)	N (%)	N (%)
Between 6 and 12 month visit	N (%)	N (%)	N (%)	N (%)
Between 12 and 18 month visit	N (%)	N (%)	N (%)	N (%)
Between 18 and 24 month visit	N (%)	N (%)	N (%)	N (%)
Between 24 and 30 month visit	N (%)	N (%)	N (%)	N (%)

[figure not shown]
Graphs by type

Dummy Figure S 1. Dummy figure to show the percentage of individuals with each reaction and severity grade, for each schedule.

[figure not shown]
Dummy Table S 2. Frequency and outcomes of unsolicited adverse events and serious adverse events

	Total (N = n)	Moderna (N = n)	Novavax (N = n)
Any AE to Day 28 (inclusive) *	N (%)	N (%)	N (%)
Any Grade 3 - 5 AE to Day 28 (inclusive) *^	N (%)	N (%)	N (%)
AE Outcome [#]			
Resolved	N (%)	N (%)	N (%)
Resolved with sequelae	N (%)	N (%)	N (%)
Ongoing	N (%)	N (%)	N (%)
Fatal	N (%)	N (%)	N (%)
Unknown	N (%)	N (%)	N (%)
Medically attended AE to Month-3 visit (inclusive)	N (%)	N (%)	N (%)
Any SAE to study-end [^]			
SOC A	N (%)	N (%)	N (%)
SOC B	N (%)	N (%)	N (%)
SOC C	N (%)	N (%)	N (%)
... for all SOCs ...	N (%)	N (%)	N (%)
SAE Outcome [#]			
Resolved	N (%)	N (%)	N (%)
Resolved with sequelae	N (%)	N (%)	N (%)
Ongoing	N (%)	N (%)	N (%)
Fatal	N (%)	N (%)	N (%)
Unknown	N (%)	N (%)	N (%)

*Unsolicited Adverse events within 28 days inclusive will be considered, rather than all adverse events before the Day-28 visit, which can occur between 28- and 35-days post-booster. ^Recurrent events in the same individual will be counted as a single event (using information from the most severe occurrence); all recurrences will be included in the line list of all adverse events. [#]Denominator is the total number of AEs/SAEs rather than the number of participants.

Dummy Figure S 2. The frequency of unsolicited adverse events to Day 28 (inclusive) by SOC, severity, and event duration. A – G are different SOCs. Colours represent event severity (Blue=Mild; Red = Severe). [Note: *This type of figure will be generated separately for each trial vaccine and presented in panels within a single figure.*]

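### SAP Table 11 row iii picks the causality category from the most severe occurrence, so the number of participants with an adverse reaction can be understated

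*SAP*

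**What the plan says.** SAP 8.2, Table 11, row iii is the endpoint "AE to Day 28 (inclusive)* [^] by causality assessment". The caret on that row leads to this footnote: "Recurrent events in the same individual will be counted as a single event (using information from the most severe occurrence". It adds that "all recurrences will be included in the line list of all adverse events". SAP 9.6 states the same rule for the safety endpoints generally, and neither place treats causality differently from severity.

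SAP 6.3, Table 4 lists adverse reactions to 28 days as an outcome and defines the term: an "adverse reaction is an adverse event with causality assessment of either Possible, Probable, or Definite".

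Protocol 8.3 requires a causality rating for each event: "The likelihood of the relationship of the AE to the trial treatment (Unrelated, Possible, Probable, Definite". It also says that "AEs characterised as intermittent will be documented for each episode". Two occurrences in one person can therefore differ in both severity and causality.

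A second footnote in Table 11 (two asterisks) covers row vii, outcomes of adverse events, and row x, outcomes of serious adverse events. For both it says that the "denominator is the total number of SAEs rather than the number of participants". The footnote to Dummy Table S 2 in SAP 10.1.2 reads "Denominator is the total number of AEs/SAEs rather than the number of participants".

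**The concern.** Taking the worst occurrence is the natural rule for a severity table such as rows ii and iv. In row iii it chooses the causality category by a different attribute, because the most severe occurrence need not be the one most plausibly caused by the vaccine.

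Example: a participant has mild dizziness on Day 2, rated Probable, and moderate dizziness on Day 20 during a viral illness, rated Unrelated. Dizziness is not on the solicited list, so both episodes belong in Table 11. The rule keeps the Day 20 episode and row iii shows Unrelated, although the participant had an adverse reaction under Table 4.

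Evaluating safety is a secondary objective. Row iii is the only row of Table 11 on causality, and Dummy Table S 2 has no causality row. A related event lost from row iii therefore appears in no planned count by arm.

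**Working it through.** **1. Direction.** Let R = 1 for an occurrence rated Possible, Probable or Definite, and R = 0 for Unrelated. The participant's true status is the maximum of R over the occurrences. The rule reports R for the most severe one.

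| Most severe | Milder | Any related | Row iii | Error |
|---|---|---|---|---|
| Related | Related | 1 | 1 | 0 |
| Related | Unrelated | 1 | 1 | 0 |
| Unrelated | Unrelated | 0 | 0 | 0 |
| Unrelated | Related | 1 | 0 | -1 |

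One member of a set cannot exceed the set's maximum, so with any number of occurrences the error is 0 or -1. When the top grade is tied and the tied ratings differ, the SAP does not say which rating is used.

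**2. Size in general form.** The documents give no event rate, recurrence rate or causality split, so there is no planned figure to reproduce. With 225 per vaccine arm (Protocol 4.1), participants missed = 225 × m × d. Here m is the share whose events are collapsed, and d is the share of those with an unrelated worst occurrence and a related milder one. Both are assumptions.

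- m = 10%, d = 10%: 225 × 0.10 × 0.10 = 2.25.
- m = 20%, d = 25%: 225 × 0.20 × 0.25 = 11.25.
- d = 0: none.

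**3. Size under the two meanings of *recurrent*.** Assume unsolicited events to Day 28 are Poisson with mean 0.6 per person, 20% are related, and severity is 60/30/10% mild/moderate/severe whatever the causality. The rates are then 0.12 related and 0.48 unrelated.

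*All of a person's events collapsed to one:*

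- At least one related event: 1 - exp(-0.12) = 0.1131, or 25.4 of 225.
- Worst related event mild: exp(-0.12 × 0.4) - exp(-0.12) = 0.9531 - 0.8869 = 0.0662. Some unrelated event moderate or severe: 1 - exp(-0.48 × 0.4) = 0.1747. Product: 0.0116.
- Worst related event moderate: exp(-0.12 × 0.1) - exp(-0.12 × 0.4) = 0.9881 - 0.9531 = 0.0349. Some unrelated event severe: 1 - exp(-0.48 × 0.1) = 0.0469. Product: 0.0016.
- Missed: 0.0116 + 0.0016 = 0.0132, or 3.0 of 225, which is 11.7% of the 25.4.
- With severity ties broken at random (simulation of 400,000 participants): about 5 of 225.

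The simulation was repeated for 0.3 to 1.0 events per person, 20% to 40% related, and related events either equally severe or milder (80/17/3%). The share missed was about 5% to 23% without ties and about 8.5% to 36% with ties split at random.

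*Only repeats of the same event collapsed*, assuming 20 equally likely, independent event terms: over the same scenarios the share missed falls to about 0.2% to 1.2% without ties and 0.4% to 2.2% with them. In the worked case that is roughly 0.15 to 0.3 of a participant per arm.

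**4. Denominators.** Row vii counts outcomes of adverse events. Read literally, its footnote divides those counts by the number of serious adverse events, so percentages could exceed 100. Dummy Table S 2 pairs adverse event outcomes with adverse events and serious adverse event outcomes with serious adverse events.

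**The case against.** The strongest reply is that *recurrent events* ordinarily means the same event coming back. Protocol 8.3 on intermittent events fits that reading. So do rows iv to vi of Table 11, which carry the same footnote and report by System Organ Class; collapsing all of a person's events to one would strip those rows of the rest. On this reading, mild related dizziness and a separate unrelated injury both remain counted, and little is lost. This largely stands as to size. Two qualifications apply. The SAP never defines the term. The 20-term calculation also ignores clustering, which would make true repeats more frequent, although repeats of one event would also tend to share a causality rating.

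It also stands that the safety summaries are descriptive, that solicited reactions are analysed separately as a primary endpoint, and that the line list in SAP 9.6 keeps each occurrence with its causality and notes adverse reactions. The DSMB reviews related events (Protocol 10.1.3) and does not depend on row iii. However, a line list is not a count by arm. The freedom in SAP 4.7 to add descriptive statistics neither changes the rule nor requires the missing count.

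A reader might infer more than the documents support:

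- *That the count is understated as a matter of course.* Loss needs discordant causality with the unrelated occurrence more severe, or tied and chosen.
- *That an early headache later followed by an unrelated one shows the fault.* A headache on Day 2 is a solicited reaction and never enters Table 11.
- *That the comparison between arms is distorted.* This would need related events to differ in severity or frequency between arms, and the documents give nothing on that.

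**Conclusion.** The concern holds as a defect in a stated rule. Row iii selects causality by severity, the resulting error in the number of participants with an adverse reaction can only be downward, and ties are unresolved. These conclusions follow from the text and rest on no assumed rate.

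The size cannot be derived from the documents. Under the ordinary same-event reading it is near zero. Under the all-events reading it is several participants per arm of 225, and every such figure depends on the assumed event rate, share related and severity split. No efficacy result or formal test is affected. The correction is still worth making because row iii is the only planned tabulation of causality and the remedy costs little. The denominator conflict is separate and minor, but it holds on the literal wording.

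**What to change.** - Confine the most-severe-occurrence rule to the severity summaries (Table 11 rows ii and iv), in both the Table 11 footnote and SAP 9.6.
- In row iii, classify each participant by the highest causality category across all their unsolicited adverse events to Day 28. Report by arm the number with at least one event rated Possible, Probable or Definite. This also removes the tie problem for causality.
- Define *recurrent*: state whether it means repeats of the same event, and at what coding level, or any further event in the same person.
- Correct the double-asterisk footnote so that row vii uses the total number of adverse events and row x the total number of serious adverse events, as in Dummy Table S 2.

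The cost is a few sentences of SAP text and a few lines of code. Causality is already recorded for every event, so no new data are needed.
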